1.9 Dose Rationale and Risk/Benefits

No human trials have yet been undertaken to evaluate the use of glyburide in reducing edema in patients with intracerebral malignancies. In Thompson's study, the human dose equivalent of glyburide would be 2.5 mg/d for a 70 kg patient (2). No adverse mouse-related hypoglycemic events were noted with comparative levels of administration. Typical oral doses of glyburide in diabetic patients range from 2.5 to 20 mg/d. The starting dose is usually a single 2.5 mg tab/day, but this can be divided into twice-per-day administrations of 1.25 mg if patients are at risk of developing hypoglycemia. Human trials in ischemic stroke currently use the IV infusion form of glyburide (RP-1127), which has less potential for hypoglycemia and is not dependent on stomach pH. In a current phase I trial evaluating tolerability in healthy volunteers, RP-1127 is given as bolus followed by 72 hour continuous infusion. No serious adverse events have been reported. Two patients with persistent hypoglycemia (at 6 mg/d and 10 mg/d) were discontinued from the study, and one patient (at 6 mg/d) had a transient asymptomatic increase in aminotransferase/alanine aminotransferase levels. In this dose-finding study, 3 mg/d seemed the safest dose to yield therapeutic serum levels while minimizing hypoglycemic risk (12).

Utilization of infusional glyburide makes sense in patient populations that are critically ill and in an intensive care settings, but trials utilizing oral glyburide are more feasible in outpatient settings. However, no data currently exists proving that oral glyburide is safe in the non-diabetic population. The Glyburide Healthy Volunteer Study is currently enrolling non-diabetic participants who take 1.5 mg/d of glyburide with breakfast. This study is designed to assess potential use of prophylactic glyburide to mitigate TBI in military personnel. As part of the trial, enrollees undergo strenuous physical activity and are monitored for hypoglycemia, dizziness, and/or confusion. Serial glucose monitoring and neuropsychological testing, as well as electrocardiographic and laboratory values, are collected and monitored during the 7 day inpatient study. These results have not yet been reported (13). As such, we aim to undertake a safety study in patients with brain metastases receiving oral glyburide followed by a randomized study to assess the effect of glyburide on peritumoral edema in patients with a high risk of edema increase after stereotactic radiosurgery.

2.0 OBJECTIVES AND ENDPOINTS

2.1 Primary Objectives

2.1.1 Pilot Portion: To determine the feasibility and safety of administering oral glyburide to non-diabetic patients receiving stereotactic radiosurgery (SRS) for newly diagnosed brain metastases.

2.1.2 Randomized Portion: To determine the number of patients with newly diagnosed brain metastases who have an increase in edema as measured on volumetric FLAIR imaging and the number of patients that require dexamethasone administration (or any corticosteroid administration with the purpose of treating cerebral edema) from the day of SRS* to one month follow-up MRI in the group receiving glyburide versus placebo.

2.2 Secondary Objectives (Randomized Portion)

2.2.1 To assess the FLAIR Volume degree of change between the treatment groups.

2.2.2 To assess the rate of symptomatic progression requiring dexamethasone (or any corticosteroid administration with the purpose of treating cerebral edema) between the treatment groups.

2.2.3 To assess differences in local control between the treatment groups.

2.2.4 To assess differences in neurologic toxicities between the treatment groups.

2.2.5 To assess differences in cardiac and hepatobiliary toxicities between the treatment groups.

2.3 Primary Endpoints

2.3.1 Pilot Portion: Occurrence of Dose Limiting Toxicities (DLTs) between the time of glyburide initiation and the time of the one month follow-up MRI.

2.3.2 Randomized Portion: Occurrence of edema increase and initiation of dexamethasone (or any corticosteroid administration with the purpose of treating cerebral edema) between the time of SRS* and the time of the one month follow-up MRI.

2.4 Secondary Endpoints

2.4.1 Pilot Portion

2.4.1.1 Time until dexamethasone initiation (or any corticosteroid administration with the purpose of treating cerebral edema) as measured between the time of SRS* and the time of the one and three month post SRS MRI scans.

2.4.1.2 Incidence of CTCAE version 4.0 reportable toxicities of grades 2-5.

2.4.1.3 Incidence of CTCAE version 4.0 reportable toxicities of grades 1-2 Cardiac Disorders or Hepatobiliary Disorders.

2.4.1.4 Cerebral edema increase as measured on FLAIR volumetric imaging, defined from MRI taken at the time of SRS* and the time of the one and three month post SRS MRI scans.

2.4.1.5 Absolute volume change of index tumor(s) that received radiosurgery as manually contoured by the radiation oncologist defined from T1 post gadolinium sequences at the time of SRS* and the time of the one and three month post SRS MRI scans.

2.4.2 Randomized Portion

- 2.4.2.1** Dexamethasone initiation (or any corticosteroid administration with the purpose of treating cerebral edema) between the treatment groups (as measured between the time of SRS* and the time of the one and three month post SRS MRI scans).
- 2.4.2.2** Rate of CTCAE version 4.0 grade 2-5 Nervous system disorder toxicities between the treatment groups.
- 2.4.2.3** Rate of CTCAE version 4.0 grade 1-5 Cardiac Disorders and Hepatobiliary Disorders between the treatment groups.
- 2.4.2.4** Comparison of mean rate of cerebral edema increase as measured on FLAIR volumetric imaging between the treatment groups (defined from MRI taken at the time of SRS* and the time of the one and three month post SRS MRI scans).
- 2.4.2.5** Comparison of median absolute volume change of index tumor(s) that received radiosurgery as manually contoured by the radiation oncologist between the treatment groups (defined from T1 post gadolinium image at the time of SRS* and the time of the one and three month post SRS MRI scans).

* Please note that the MRI may be performed within 21 days prior to SRS treatment only if the patient is being treated with linac-based radiosurgery and it is not standard of care to complete a MRI on the day of SRS (as it is with gamma knife).

3.0 PATIENT SELECTION

3.1 Conditions for Patient Eligibility

- 3.1.1** Patients with newly diagnosed brain metastases deemed to be eligible for radiosurgery.
 - 3.1.1.1** Prior whole brain RT and radiosurgery (to areas outside of the newly diagnosed brain metastases requiring radiosurgery) is allowed
- 3.1.2** Subject must have cytologically or histologically confirmed malignancy (this is the original malignancy, not the brain metastases).
- 3.1.3** A diagnostic contrast-enhanced MRI of the brain must be performed within 60 days prior to registration. The contrast-enhancing intraparenchymal brain tumor must be well visualized.
- 3.1.4** History and physical with neurological examination, height, and weight within 14 days prior to registration.
- 3.1.5** No dexamethasone use (or any other corticosteroid use with the purpose of treating cerebral edema) starting 5 days prior to SRS. Patients may be tapered to meet this criterion if deemed safe by the treating physician.
- 3.1.6** Women of child-bearing potential (e.g. not post-menopausal or permanently sterilized women) must have a negative pregnancy test obtained within 14 days prior to registration. This is to prevent potential harm to the fetus by glyburide and radiotherapy.
- 3.1.7** Age \geq 18 years of age.
- 3.1.8** Complete Blood Count (CBC) with differential and a Comprehensive Metabolic Panel (CMP) including Liver Function Tests (LFTs) obtained within 14 days prior to registration and meeting the following requirements:
 - Creatinine Clearance \geq 50 mL/min (by Cockcroft-Gault Equation).

- Total Bilirubin < 1.5 x the upper limit of normal (ULN).
- ALT and AST ≤ 2.5 x ULN.
- Glucose ≥ 80 mg/dL.
- Hemoglobin ≥ 7 mg/dL.
- Absolute Neutrophil Count > 100 cells/mm³.

3.1.9 For the Randomized Portion only:

3.1.9.1 Subject must have at least 2 of the following risk factors:

- Pretreatment Edema/Tumor ratio (≥ 35:1) as contoured on a baseline MRI obtained at most 60 days prior to registration. Patients are allowed to have Whole Brain Radiotherapy (WBRT) or corticosteroid use between the time of pretreatment MRI and SRS (as long as the corticosteroids can be safely tapered at least 5 days prior to the treatment planning MRI and WBRT is at least 4 days prior to registration).
- Greater than 40 pack year history of smoking cigarettes.
- Whole Brain Radiotherapy at least 4 days and no more than 1 year prior to registration.
- RPA Class III.

3.1.10 For the Pilot Portion, it is not required that patients have the risk factors mentioned in 3.1.9.

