1.4 Investigational Agent – Glyburide (non-micronized)

Glyburide tablets contain glyburide, which is an oral blood-glucose-lowering drug of the sulfonylurea class (7). Glyburide is a white, crystalline compound, formulated as glyburide tablets of 1.25, 2.5, and 5 mg strengths for oral administration. Inactive ingredients include colloidal silicon dioxide, magnesium stearate, microcrystalline cellulose, pregelatinized starch, and sodium starch glycolate. In addition, the 2.5 mg tablet contains D&C yellow No. 10 Aluminum Lake and the 5 mg tablet contains FD&C Blue No. 1 Aluminum Lake and D&C Yellow No. 10 Aluminum Lake. The chemical name for glyburide is 1-[[p-[2-(5-chloro-o-anisamido)-ethyl]phenyl]-sulfonyl]-3-cyclohexylurea and the molecular weight is 493.99. The structural formula is represented below:

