1.8 Study Rationale

The most common side effect of glyburide is hypoglycemia. Sulfonylureas carry a rare but serious risk of increased cardiovascular mortality. Although the risk of cardiovascular mortality in patients receiving tolbutamide, a first-generation sulfonylurea, was 2.5 times that of patients treated with diet alone, subsequent studies have indicated that glyburide is not associated with an increased risk of cardiovascular events. A rare sulfonylurea-associated risk is hemolytic anemia in patients with G6PD deficiency and, in even more rare instances, in those without.

In contrast, dexamethasone causes disturbances in glucose metabolism in approximately 50% of patients, in addition to immunosuppression, femoral avascular necrosis, thrush, psychiatric disorders, and Cushing syndrome, among others.

In addition to a favorable side effect profile, the cost/benefit considerations of glyburide over alternatives merit consideration. The cost of a 30 day supply of glyburide is approximately \$30, compared with \$22 for dexamethasone. The cost of bevacizumab is approximately \$9,000/month.

Stereotactic radiosurgery (SRS) for brain metastases results in an approximately 5% incidence of radiation induced neurologic morbidity. Current interventional options include corticosteroids, pentoxifylline and vitamin E, surgery, hyperbaric oxygen, anticoagulation, and interstitial laser thermal therapy. More recently, bevacizumab has been shown to reduce T2/fluid-attenuated inversion recovery volumes on MR in patients with presumed SRS-induced radiation effects. A 90% improvement in neurologic symptomatology was noted; however, 61% of those patients experienced a return of neurologic symptomatology after discontinuation of anti-VEGF therapy. Because of the side-effect profile and high cost of anti-VEGF therapies, glyburide becomes an intriguing alternative as either prophylaxis against potential development of edema induced from radiotherapy or as a treatment alternative for existing edema that is at risk of becoming more significant with radiotherapy (1).

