3.2 Conditions for Patient Ineligibility

- 3.2.1** Known sulfonylurea treatment within 7 days prior to registration. Sulfonylureas include glyburide/glibenclamide (Diabeta, Glynase); glyburide plus metformin (Glucovance); glimepiride (Amaryl); repaglinide (Prandin); nateglinide (Starlix); glipizide (Glucotrol, GlibeneseR, MinodiabR); gliclazide (DiamicronR); tolbutamide (Orinase, Tolinsase); and glibornuride (Glutril).
- 3.2.2** Diffuse Leptomeningeal metastases.
- 3.2.3** Known allergy to sulfa or specific allergy to sulfonylurea drugs.
- 3.2.4** Use of VEGF inhibitors within 10 days prior to registration.
- 3.2.5** Allergy to gadolinium.
- 3.2.6** Type 1 diabetes mellitus or Type 2 diabetes mellitus actively receiving treatment.
- 3.2.7** Cognitive impairment that precludes a patient from acting as his or her own agent to provide informed consent.
- 3.2.8** Concurrent use of Bosentan.
- 3.2.9** Any major medical illnesses or psychiatric impairments that in the treating physician's opinion will prevent administration or completion of protocol therapy (which may include patients who are elderly, debilitated, or malnourished persons and/or those with renal, hepatic or adrenal insufficiency).
- 3.2.10** Pregnant or breast feeding women due potential damage to the fetus.
- 3.2.11** Inability to undergo MRI or SRS (e.g. due to safety reasons such as presence of a pacemaker).
- 3.2.12** Deemed by the treating physician to be unable to eat regular meals.

3.2.13 Patients currently on beta blockers.

3.2.14 Patient with a known diagnosis of ongoing alcoholism/alcohol abuse.

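### The hemoglobin entry limit in section 3.1.8 is written in mg/dL, so read literally it cannot exclude any patient

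*Combined protocol and SAP*

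**What the plan says.** Section 3.1.8 lists laboratory conditions for entry. The blood count and metabolic panel must be "obtained within 14 days prior to registration and meeting the following requirements". One of the conditions is "Hemoglobin ≥ 7 mg/dL". The line directly above it is "Glucose ≥ 80 mg/dL".

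The condition is binding. Sections 5.1.1 and 5.2.1 allow enrollment only when every eligibility criterion is met, and the enrollment date is the day a verifying physician signs the Eligibility Checklist. Section 3.1.9 confines only the risk-factor requirement to the Randomized Portion, so the laboratory limits in 3.1.8 apply to both portions.

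No other section states a hemoglobin limit, and g/dL appears nowhere in the documents. The exclusions in section 3.2 do not mention anemia. The nearest is 3.2.9, which excludes patients with "Any major medical illnesses or psychiatric impairments that in the treating physician's opinion will prevent administration or completion of protocol therapy". It is a matter of judgment and gives no hemoglobin value.

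**The concern.** The usual laboratory unit for hemoglobin is grams per decilitre. A limit of 7 in milligrams per decilitre lies far below any value a living patient could have, so the test is always passed. A numeric safety condition that must be verified before each enrollment would then do nothing.

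Two things are at stake. If the text is followed, a severely anemic patient satisfies this criterion. If staff instead substitute the unit they expect, a patient turned away on hemoglobin has met the protocol's literal requirement, and an audit of eligibility has no correct text to check against. In both cases the written rule and the rule presumably intended differ.

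**Working it through.** The plan has no calculated figure here to reproduce. The check is a unit conversion and a comparison.

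**Inputs**
- Written limit: 7 mg/dL (section 3.1.8).
- Conversion: 1 g/dL = 1000 mg/dL.
- Clinical hemoglobin range: about 3 to 18 g/dL. This is an assumption, not a figure from the documents. A value of 1 g/dL is added as an extreme case.

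**Step 1. Convert the limit.** 7 mg/dL ÷ 1000 = 0.007 g/dL.

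**Step 2. Compare patient values with it.** Ratio = hemoglobin in g/dL ÷ 0.007.

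| Hemoglobin (g/dL) | In mg/dL | Ratio to written limit | Excluded as written? |
|---|---|---|---|
| 1 | 1,000 | 143 | No |
| 3 | 3,000 | 429 | No |
| 5 | 5,000 | 714 | No |
| 7 | 7,000 | 1,000 | No |
| 12 | 12,000 | 1,714 | No |
| 18 | 18,000 | 2,571 | No |

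Every value passes. Over the assumed range, patient values are about 430 to 2,570 times the written limit. The result does not depend on where the range is drawn, since even 1 g/dL passes by a factor of 143.

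**Step 3. Size of the unit error.** If the number 7 was intended and only the unit is wrong, the limit in mg/dL would be 7 × 1000 = 7,000, which is 1000 times the written one. Values below 7 g/dL (1, 3 and 5 in the table) would then be excluded, whereas the written rule excludes none of them. This shows only what changing the unit alone would do. The documents do not establish what limit was intended.

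**Step 4. Look for a correction elsewhere.** There is none: 3.1.8 is the only hemoglobin limit, and 3.2.9 supplies no number. The glucose line just above uses mg/dL, a usual unit for glucose, so a carried-over unit is a plausible explanation, though the documents do not confirm it.

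**Step 5. Effect on the statistics.** Hemoglobin does not enter the primary endpoint (9.1), the analysis (9.3) or the sample size (9.5), so none of those figures changes.

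**The case against.** The strongest reply is that this is a typing slip with little practical effect. Clinical staff reading a blood count would probably take the 7 in the unit on the laboratory report, and nothing in the documents shows that a severely anemic patient would be enrolled because of it. That is fair as a prediction of conduct, and it keeps the severity low. It does not make the text right, because staff would be applying a limit the protocol does not contain.

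Several stronger readings are tempting, and the documents do not support them.

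- **That entry is unguarded against anemia.** Only this criterion is inert. A blood count is required before registration, so the physician sees the hemoglobin and can use 3.2.9. Counts are repeated at one week, one month and three months after radiosurgery. What stands is that none of these carries a hemoglobin value.
- **That the slip disables a safeguard against drug-induced hemolysis.** Glyburide is described in 1.4 as a drug "which is an oral blood-glucose-lowering drug of the sulfonylurea class", and section 1.8 says "A rare sulfonylurea-associated risk is hemolytic anemia in patients with G6PD deficiency and, in even more rare instances, in those without". The protocol thus calls the risk rare, and no section says the hemoglobin limit is there because of it.
- **That the absence of a G6PD requirement is part of the same error.** A hemoglobin floor does not screen for G6PD deficiency. Whether to test for it is a separate design question and is not evidence about the unit.
- **That the limit is 1000-fold below every clinical value.** The factor of 1000 is the unit error. The gap to a patient's value varies, as the table shows.
- **That the Eligibility Checklist is also wrong.** The checklist is not in the documents, so its wording is unknown.

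**Conclusion.** The criterion is wrong as written, at low severity. Section 3.1.8 sets a hemoglobin limit equal to 0.007 g/dL, which no patient can fail. The unit error is a factor of 1000 if g/dL was meant. That g/dL was meant is an inference from ordinary laboratory practice; that the written criterion excludes nobody needs only the unit conversion and the fact that any patient's hemoglobin is far above 0.007 g/dL.

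This is more than a slip in background text, because the line is an operative condition for enrollment and nothing else in the documents supplies the missing limit. How many patients it would affect cannot be estimated, since it depends on how staff read the line and on what the checklist says.

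**What to change.** Correct the unit in section 3.1.8 to the one in which the laboratory reports hemoglobin, and have the sponsor confirm the intended numeric limit; this review does not propose one. Check whether the Eligibility Checklist repeats mg/dL, and correct it in the same step if it does.

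The cost is a one-word protocol correction, possibly matched in the checklist. No statistical section needs revision.

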4.2.2 Within 14 days prior to registration

- 4.2.2.1** History and Physical with height, weight, neurological exam and corticosteroid use documentation. If using dexamethasone (or any other corticosteroid with the purpose of treating cerebral edema), must implement a plan to have this safely discontinued by 5 days prior to SRS.

- 4.2.2.2** Complete Blood Count (CBC) with differential and a Comprehensive metabolic panel (CMP) including Liver Function Tests (LFTs).
- 4.2.2.3** Pregnancy test for women of child-bearing potential.

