4.2.3 Within 21 days prior to SRS

- 4.2.3.1** Follow-up brain MRI with and without contrast. T1-weighted, T2, and/or FLAIR MRI of the brain (maximum slice thickness 5mm). FLAIR imaging is preferred.
 - 4.2.3.1.1** T1 post gadolinium sequence will be imported into the Eclipse treatment planning system and the radiation oncologist (who will be blinded to the patient's investigational medication) will contour the enhancing tumor that received the prescribed dose of SRS.
 - 4.2.3.1.2** FLAIR sequence will be imported into the Eclipse treatment planning system. FLAIR volume will be automatically calculated using "Region Growing" on Eclipse (Appendix I). The automated contours will be verified and modified as needed by the radiation oncologist who will be blinded to the patient's investigational medication.

4.2.4 5-9 days prior to SRS

- 4.2.4.1** Randomization will occur (can be any time after registration/study entry and up until 5-9 days prior to SRS).
- 4.2.4.2** Documentation of corticosteroid use/no dexamethasone (or any other corticosteroid with the purpose of treating cerebral edema) use.
- 4.2.4.3** Give patient a sufficient supply of investigational medication: either non-micronized Glyburide tablets (1.25 mg) or placebo, to be taken orally twice a day (in the morning with breakfast and in the evening with dinner). Missed doses will not be made up. Patient, physicians, and the study team will be blinded to the investigational medication. Patient should be instructed to begin investigational medication at least 5 days prior to SRS and continue investigational medication until the evening dose of the one month post SRS MRI scan.
- 4.2.4.4** Provide patient with study supplies that include a medication/blood glucose log (for recording time of taking the investigational medication as well as time and value of blood glucose draws), a blood glucose monitor, and handouts for education purposes. The patient will be educated on how to measure and record blood glucose values (see Appendices II-VI).
- 4.2.4.5** Patient should begin fingerstick glucose draws once a day beginning the day of investigational medication initiation (in the morning before breakfast [fasting]). Please see section 5.4.2 for further details. An additional fingerstick glucose draw will be taken by the nurse/research team member at this visit.

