4.2.9 Conditions for early patient stopping of investigational medication

4.2.9.1 A dose limiting toxicity (DLT) is reached. See section 5.3.2.

4.2.9.2 Patient requires corticosteroid administration after registration but prior to SRS, please note these patients will be deemed inevaluable.

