5.2 Randomized Portion

The Randomized Portion of this study will only proceed if there have been 10 evaluable patients on the Pilot Portion (this includes both full dose glyburide and reduced dose glyburide, if applicable) and it is deemed safe. All data will be reviewed and approved by the Data Safety Monitoring/Quality Assurance Committee (DSMQAC) after the Pilot Portion and prior to starting the Randomized Portion at the safe dose as determined by the Pilot Portion. The Randomized Portion will enroll 40 evaluable patients. Inevaluable patients will be replaced.

Patients with brain metastases, who are not taking dexamethasone (or any other corticosteroid with the purpose of treating cerebral edema) within 5 days prior to SRS, after informed consent, will be randomized to a blinded investigational medication:

- Non-Micronized glyburide (1.25 mg po BID) should begin at least 5 days prior to SRS to be taken until the evening dose on the day of the one month follow-up MRI.
OR
- Placebo (1 tablet po BID) should begin at least 5 days prior to SRS to be taken until the evening dose on the day of one month follow-up MRI.

All patients will receive linac-based radiosurgery, which must be initiated at least 5 days after starting the investigational medication (can be more for patients being treated with linac-based radiosurgery where the MRI may be done within 21 days prior to SRS treatment).

For treatment planning and at the time of the one and three month follow-up appointments, the patient must undergo a brain MRI with and without contrast. T1-weighted, T2, and/or

FLAIR MRI of the brain (maximum slice thickness 5mm). FLAIR imaging is preferred. The treatment planning MRI may be done within 21 days prior to SRS treatment only for patients being treated with linac-based radiosurgery where it is not standard of care to complete a MRI on the day of SRS (as it is with gamma knife).

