T1 post-gadolinium sequences and FLAIR axial sequences from the treatment planning MRI (see note above regarding linac-based radiosurgery patients) and at the one and three month follow-up appointments will be imported into the Eclipse treatment planning system. On the T1 post gadolinium sequences, the radiation oncologist will contour the enhancing tumor that received the prescribed dose of SRS. Using the FLAIR sequences Eclipse will automatically calculate FLAIR volume using “Region Growing” (Appendix I). The automated contours will be verified and modified as needed by the radiation oncologist. Physicians, patients, and the study team will be blinded to the patient’s investigational medication.

5.2.1 Patients can only be enrolled after all eligibility criteria are met. The date of registration/enrollment/study entry is considered to be the day the Eligibility Checklist is signed by the verifying physician and should be no later than 5-9 days prior to SRS. Once a patient is enrolled, a unique case number will be assigned to the patient and blinded randomization will occur. Patients will be randomized by the UAB Investigational Drug Services (IDS) Pharmacy, who will hold the blind for this study.

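### The five steroid-free days are counted back from SRS in 3.1.5, 4.2.2.1 and 5.2 but from the planning MRI in 3.1.9.1, so the baseline edema scan can be taken on dexamethasone

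*Combined protocol and SAP*

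**What the plan says.** Two different events anchor the steroid-free interval.

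- **Anchored to SRS.** Section 3.1.5 requires "No dexamethasone use (or any other corticosteroid use with the purpose of treating cerebral edema) starting 5 days prior to SRS" and lets patients be tapered to meet this. Section 4.2.2.1 says that a patient on steroids at work-up "must implement a plan to have this safely discontinued by 5 days prior to SRS". The opening of 5.2 uses the same anchor, as do 4.1.2.1 and 5.1 for the pilot.
- **Anchored to the planning MRI.** The edema/tumor-ratio bullet of 3.1.9.1 permits steroids between the pretreatment MRI and SRS "as long as the corticosteroids can be safely tapered at least 5 days prior to the treatment planning MRI".

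The timing of the planning MRI is given by the heading "4.2.3 Within 21 days prior to SRS". Section 5.2 limits that window to linac patients who would not routinely have an MRI on the day of SRS, but it also says "All patients will receive linac-based radiosurgery, which must be initiated at least 5 days after starting the investigational medication", so the window is potentially open to everyone.

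This scan is the starting point for edema change in 8.3.4, 8.4.4 and secondary endpoint 2.4.2.4. Section 8.4.4 scores a rise of at least 5.0% by the one-month MRI as an increase, and 8.4.6 names that increase as the randomized portion's primary endpoint. Section 9.1.2 defines treatment failure differently: edema that increases enough to require steroids, or a glyburide-related death.

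**The concern.** An edema volume measured on dexamethasone is likely to be lower than the same patient's volume off it. The documents accept this: Section 1.1 gives glucocorticoids as the standard treatment for symptomatic edema, and 9.5.2 says steroid use in the historical series probably lowered the number of patients with an edema increase. If the baseline scan is taken on steroids and the one-month scan is not, part of any measured rise may reflect withdrawal, not radiosurgery or study drug.

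Events of that kind would be expected in both arms. They add failures unrelated to treatment and shrink the difference that the trial is sized to detect. With 20 patients per arm and no stratification by prior steroid use described, the share of tapering patients could also differ between arms by chance.

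**Working it through.** **1. Date arithmetic.** Take a planning MRI on day -d, with SRS on day 0. Section 3.1.9.1 requires steroids off by day -(d+5). Sections 3.1.5 and 4.2.2.1 require them off by day -5. The difference is (d+5) - 5 = d days.

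| Planning MRI | Off by, 3.1.9.1 | Off by, 3.1.5 | Difference |
|---|---|---|---|
| day -21 | day -26 | day -5 | 21 days |
| day -14 | day -19 | day -5 | 14 days |
| day -7 | day -12 | day -5 | 7 days |
| day 0 | day -5 | day -5 | 0 |

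Under 3.1.5 alone, a scan on any of days -21 to -6 can be taken on dexamethasone.

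**2. Whether another rule closes the gap.** Section 4.2.9.2 reads "Patient requires corticosteroid administration after registration but prior to SRS, please note these patients will be deemed inevaluable". It starts at registration, which "should be no later than 5-9 days prior to SRS", so the planning MRI can come first. Section 8.2.1 concerns steroids initiated before SRS, not a taper already under way, which 3.1.5 permits. Neither closes it.

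**3. How little suppression is needed.** Section 8.4.4 calls the 5.0% an absolute percentage, which is not clear for a volume. Read as relative change, a baseline lowered by 1 - 1/1.05 = 4.8% is enough: returning to the unsuppressed volume alone meets the rule.

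**4. The plan's own power.** Inputs from 9.3.2 and 9.5.2: 20 per arm, success 50% vs 75%, one-sided p of 0.30 or less, exact test. Enumerating both binomials with Fisher's exact test gives 0.802, which reproduces the stated 0.80.

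**5. Illustrative loss if the 8.4.6 definition governs.** Let q be the share of patients with a suppressed baseline, set at 20%. This is an assumption; the documents give no figure.

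*Mild model.* A fraction r of affected would-be successes become failures in both arms. Success rates are 0.50(1 - qr) and 0.75(1 - qr).

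| r | Placebo | Glyburide | Power |
|---|---|---|---|
| 20% | 48.0% | 72.0% | 0.78 |
| 30% | 47.0% | 70.5% | 0.77 |
| 50% | 45.0% | 67.5% | 0.75 |

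*Severe model.* Affected patients fail with the same probability f in both arms, so they carry no treatment difference. Success rates are 0.50(1 - q) + (1 - f)q and 0.75(1 - q) + (1 - f)q. With f = 1 these are 40% vs 60%, and power is 0.69. With f = 0.8 they are 44% vs 64%, and power is again 0.69. The result is driven by the missing treatment difference, not by f.

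**The case against.** The strongest objection is that the statistical section counts something else. Under 9.1.2 a silent 5% rise is a success, and 8.2.1 reserves steroids for symptomatic patients with imaging evidence of increasing edema whose physician judges them necessary. The 50% and 75% are success rates from Section 9. A reader might infer that the primary analysis, as it stands, loses power. The documents do not support that without a condition: it follows directly only if 8.4.6 governs, and 8.4.6 and 9.1.2 disagree. This part of the objection stands.

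Second, the documents do not show that withdrawal before SRS leaves a rise still present at one month, nor how many patients will be tapering. The planned 50% placebo success is also already below the 65% (100% - 35%) implied by the edema-increase risk quoted in 1.8 for patients with two or more risk factors, so it may absorb some off-steroid increase. This stands too, and is why the power figures are only illustrations. The 0.69 lies at the severe end because it removes any glyburide effect in affected patients.

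Third, the rules are nested: a patient steroid-free 5 days before the planning MRI is also steroid-free 5 days before SRS. The 3.1.9.1 sentence could be read as covering all randomized patients. Its position inside one risk-factor bullet makes that uncertain. A patient who qualifies through smoking, prior WBRT or RPA class, and every pilot patient, is plainly bound only by the SRS-based rule.

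Finally, steroid use is already documented at work-up, 5-9 days before SRS and on the day of SRS. No stop date is specified, and nothing ties the record to the day of the planning MRI.

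**Conclusion.** The inconsistency is real. Following the plan as written, the edema baseline can be obtained while a patient is on dexamethasone. The secondary comparison in 2.4.2.4 is exposed in any case; the primary endpoint is exposed directly under 8.4.6, and under 9.1.2 only when the rise leads to steroid initiation.

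The expected effect is dilution, with possible chance imbalance. A reader might infer systematic bias toward one arm, but randomization gives no reason to expect that.

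The size is unknown. With 20% of patients affected, power moves from 0.80 to about 0.75-0.78 if 20-50% of affected would-be successes become failures, and to 0.69 if affected patients carry no treatment difference. Those shares are assumptions, and the figures apply to the primary analysis only if the radiographic definition is used. A reader might also infer that the 3.1.9.1 interval is the correct one. The documents do not settle that, and the choice is the sponsor's.

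**What to change.** 1. Reconcile 3.1.5, 4.2.2.1, 5.2 and 3.1.9.1 to one stated anchor, chosen by the sponsor, and state how it relates to the MRI used as the edema baseline. Align 4.1.2.1 and 5.1 for the pilot.
2. Record steroid status and the date of the last steroid dose at the planning MRI.
3. Prespecify a sensitivity analysis of the edema endpoints that excludes, or adjusts for, patients who were on steroids or within 5 days of them at that scan.
4. Note the conflict between 8.4.6 and 9.1.2 and state which defines the primary endpoint, since that decides how far this point reaches.

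The cost is clarified wording, one extra data item and one extra analysis. Sample size and the primary test do not change.
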